The University of Texas Medical Branch

Title: Comparison of blood loss and intraoperative visibility between Labetalol and Esmolol: A randomized controlled trial

Principal Investigator: [name], MSCR, MBA

Funding Sponsor: Departmental

IND number: N/A

Version number and date: 1.0_01/23/2016

1. Introduction and Purpose

Bleeding during endoscopic sinus surgery (ESS) affects the ability of the surgeon to identify key structures such as the skull base, orbit, nerves and major vessels. Rhinologists have examined multiple ways to decrease intraoperative bleeding as well as improve endoscopic visibility.

This study hypothesizes that intraoperative blood pressure control with esmolol decreases blood loss and improves operative visibility during ESS as compared to labetalol. The effect will be objectively studied by comparing estimated blood loss and intraoperative visibility utilizing validated intraoperative bleeding/ visibility scores. In addition, patients will be stratified in accordance to their severity of their disease according to their Lund Mackay scores based on their CT scan findings that are routinely obtained prior to surgery.

The short half-life and the ability of continuous infusion of esmolol provides a tighter control of intraoperative blood pressure. Additionally, its selective beta blockade avoids antagonizing the effect of the topical epinephrine vasoconstrictor that is used intraoperatively during ESS.

If the study demonstrated a significant difference between the groups, it would potentially affect our selection of beta blockers during ESS. The potential benefits include providing safe, complete surgery and potentially decreasing cost. The complications that could potentially arise from poor intraoperative visibility include CSF leak and orbital injuries that could lead to lead to blindness.

2. Background

During ESS, bleeding from the mucosal surfaces often interferes with visualization of the anatomy and increases the small risks of serious complications such as injuring the skull base leading to a cerebrospinal fluid leak or an injury to the eye. Additionally, the bleeding interferes with visualization during the procedure and a reduction of the bleeding would result in greater ease and thoroughness of the sinus surgery.

Historically, several ways have been used to decrease intraoperative bleeding. Controlled hypotension (keeping the mean arterial pressure between 50 and 60) has been used using either the anesthetic agents alone or using either sodium nitroprusside or esmolol drips [1-3]. The use of these medications increases the risk of serious side effects such as cyanide toxicity and myocardial depression. Recent studies have shown that controlled hypotension is associated with increased morbidity and mortality. The latter was found to be in the range of 20 to 60 deaths in 100,000 patients mainly as a consequence of ischemic organ failure [4]. There is also good evidence that decreasing the MAP below 70 can even increase intraoperative bleeding due to local arteriolar vasodilatation which results from decreased blood flow to the tissues, increased local carbon dioxide concentration and decreased pH.

[3,5]. Another mechanism that can explain this is an increase in cardiac output during controlled hypotension resulting from reflex tachycardia especially with the use of a pure vasodilator like sodium nitroprusside [6].

There are multiple factors which contribute to blood loss during surgery, including, but not limited to surgical and anesthetic technique. At the University of Texas Medical Branch, the endoscopic surgical technique is fairly uniform and comparable to practices throughout the world. Most of the endoscopic sinus surgery is performed under general anesthesia. There is a suggestion among ENT physicians and anesthesiologist that different blood pressure medications affect intraoperative visibility and possibly lead to less intraoperative blood loss. It is also thought that intraoperative topical decongestants (specifically epinephrine) work by binding to alpha receptors. Labetalol, which is an alpha and beta blocker, may interfere with the effect of this topical decongestant. [7-9] The goal of this investigation is to formally evaluate this notion utilizing two very commonly used blood pressure medications: Labetalol and esmolol. This study does not use any medications that are not routinely used during endoscopic sinus surgery at the University of Texas Medical Branch.

3. Concise Summary of Project:

Subjects who are scheduled for routine endoscopic sinus surgery will be recruited (n=40). The subjects in this prospective study will be randomized to either receive labetalol or esmolol. Current standard of care in preventing hypertension during sinus surgery due to stimulation and injection and application of sympathetic agents includes, narcotic administration, increasing volatile agent (Sevoflurane), esmolol, labetalol and other agents (hydralazine, nicardipine and nitroprusside). It is not known the impact these anti-hypertensive agents have on blood loss or blood in surgical field.

Intraoperatively, topical epinephrine pledgets will be used for decongestion similar to what is done routinely in endoscopic sinus surgery.

Intraoperative visibility will be scored utilizing two validated endoscopic visibility scores. In addition, at the end of surgery the estimated blood loss will be calculated by subtracting the amount of irrigation used during surgery from the amount of blood in the suction canisters.

In addition, the surgical video will be recorded and the intraoperative visibility will also be recorded by an independent observer.

In addition to the demographics and our primary outcome, secondary outcomes will be collected including duration of anesthesia, duration of surgery, final CO₂, postoperative bleeding, visit to the ED following discharge, need for medical attention following discharge, surgeon satisfaction on a likert scale (1-10), need for surgical re-intervention, and pain score after surgery, as well as time spent in recovery, use of anti-emetics postop, and nurses notes on as regards to pain and recovery.

Subjects may be excluded from the study if the anesthesiologist deemed it necessary that the protocol drug can not be used on the patient for any reason. Otherwise, it is expected that the surgeries will be routinely performed and the study outcome

variables do not interfere with the routine.

4. Study Procedures:

This will be a prospective randomized study comprising subjects (n=40) over 18 years of age scheduled for ESS. The inclusion criteria will be male or female patients with ASA physical status 1 (normal otherwise healthy patient) or 2 (patient with mild systemic disease) and patients who have chronic sinusitis with or without nasal polyps. Exclusion criteria include: pregnancy, asthma, obstructive pulmonary diseases, sinus bradycardia and severe bradycardia, sick sinus syndrome, heart failure, end-stage renal disease, stroke, diabetes mellitus, preoperative use of nonsteroidal anti-inflammatory medications (NSAIDS) or aspirin (ASA) within the last week, and a body mass index (BMI) greater than 40. Additionally, any patient that the anesthesiologist deems unfit for randomization will also be excluded.

We will randomize the patients in blocks of 4 to determine the impact of a specific study drug (either esmolol (n=20) or labetalol (n=20) along with sevoflurane to control blood pressure on bleeding. The patients will be classified according to their Lund Mackay scores, which will be obtained from their routine CT scan performed prior to their surgery.

Written informed consent will be obtained. On arrival to the operating room, all the patients will be monitored as per usual anesthesia routine. Patients in both groups will be induced using 1-2 mg midazolam PRN anxiety, 1-3 mcg/kg fentanyl, 20-40 mg lidocaine, 1-2 mg/kg propofol, and 0.05-0.1 mg/kg vecuronium. Thereafter, maintenance with general anesthesia will receive 1-2% of sevoflurane (end expired). Both groups may receive fentanyl throughout the case at the discretion of the anesthesiologist. The dose of fentanyl is not to exceed 5 mcg/kg. The patient's mean arterial blood pressure (MAP) will be maintained at 70-80 mm Hg (80 for hypertensive patients) by first adjusting the sevoflurane concentration within their range (between 1-2 percent for the sevoflurane. If sevoflurane is maximized (Fe sevo >2%) and the target MAP is not achieved, then the patients will receive either esmolol or labetalol (study drug will be blinded for surgeon).

The surgical procedure will not be altered. All patients will be placed supine with 6 degrees head up the entire procedure. Local vasoconstriction will be performed first with bilateral endonasal application of oxymetazoline soaked pledgets for 2 minutes. This is followed by placing topical epinephrine pledgets (1:1000) throughout the duration of the case. Our primary Outcome measures will include 1) intraoperative visibility utilizing two validated bleeding scores (Wormald and Boezart score) intraoperative visibility (1 minute, and every 20 minutes thereafter) 2) estimated blood loss at the of end of surgery which will be calculated by subtracting the amount of irrigation used from the total blood in the suction canisters. Blood loss will be evaluated by the blinded rhinologist ([name]) and an independent observer who will review the un-identified endoscopic surgical videos.

In addition to the demographics and our primary outcome, secondary outcomes will be collected including duration of anesthesia, duration of surgery, final CO₂, postoperative bleeding, visit to the ED following discharge, need for medical attention following discharge, need for surgical re-intervention, Bispectral index (**BIS**) monitoring intraoperatively (taped on patient forehead), surgeon satisfaction score on likert scale (1-10), and pain score after surgery, as well as time spent in recovery, use of anti-emetics postop, and nurses notes on as regards to pain and recovery. All the medications used in this study are used as part of the standard of care when patients develop high intraoperative blood pressure as a result of the usage of the topical decongestants.

Blood pressure control medications:

Labetalol is a mixed adrenergic receptor antagonist (beta 1 > alpha 1 blocker). If randomized, the anesthesiology investigator will obtain 3 bottles of labetalol (100 mg in 10 mL). Per protocol, aliquots of 10-30 mg of labetalol will be administered SIVP if MAP > 80 and sevoflurane [2%]. Initial dose will be 20 mg (within 2 min), followed by infusion of 0.25-0.5 µg/min. Maximum dose = 300 mg for case duration. If maximum dose is achieved, other agents per discretion of the anesthesiologist will be administered.

Esmolol is a specific beta adrenergic antagonist (beta 1 >> beta 2). If randomized, the anesthesiology investigator will obtain a 2500 mg in 20 mL vial. Esmolol will be diluted in 250 mL 0.9% NaCl to achieve a concentration of 10 mg/mL. Per protocol, an infusion of esmolol at a rate of 0.1 mg/kg/min if MAP > 80 and sevoflurane [2%]. The dose can be titrated up to 0.3 mg/kg/min. If after 30 min, the esmolol dose is >0.3 mg/kg/min other agents per discretion of the anesthesiologist will be administered.

5. Sub-Study Procedures:

N/A

6. Criteria for Inclusion of Subjects

The inclusion criteria will be male or female patients with ASA physical status 1 (normal otherwise healthy patient) or 2 (patient with mild systemic disease) and patients who have chronic sinusitis with or without nasal polyps and who are scheduled for a routine ESS.

7. Criteria for Exclusion of Subjects

Exclusion criteria include: pregnancy, asthma, obstructive pulmonary diseases, sinus bradycardia and severe bradycardia, sick sinus syndrome, heart failure, end-stage renal disease, stroke, diabetes mellitus, preoperative use of nonsteroidal anti-inflammatory medications (NSAIDs) or aspirin (ASA) within the last week, and a body mass index (BMI) greater than 40. Subjects may be excluded from the study if the

anesthesiologist deemed it necessary that the protocol drug cannot be used on the patient for any reason. Otherwise, it is expected that the surgeries will be routinely performed and the study outcome variables do not interfere with the routine.

8. Sources of Research Material

Intraoperatively, a bleeding score will be used (validated questionnaire) based on the visibility. In addition, at the end of the surgery, the estimated blood loss will be calculated. All other secondary outcomes will be collected following the completion of surgery. These will be obtained from the medical record (duration of anesthesia, duration of surgery, final CO₂, Bispectral index (**BIS**) monitoring, postoperative bleeding, visit to the ED following discharge, need for medical attention following discharge, need for surgical re-intervention, and pain score after surgery, as well as time spent in recovery, use of anti-emetics postop, and nurses notes on as regards to pain and recovery).

9. Recruitment Method and Consenting Process:

The informed consent for the study will be obtained either in the preoperative clinic visit or on the day of the surgery in the pre-operative holding area. Informed consent for the study will be separate from the surgical consent. The name of the attending surgeon will be written on the study consent together with the name of the attending anesthesiologist. The informed consent will then be included in the patients' charts.

10. Potential Risks:

The risks and benefits of the study will be discussed with the patient on obtaining written informed consent. Consent for surgery and anesthesia will be done as usual. The study adds no risks above those associated with risks of surgery and risk of anesthesia. Neither anesthetic technique used here breaches the standard of care nor is the surgical technique not altered. There is no clear evidence of any difference in between the two groups in the literature in regards to their effect on recovery time or their gastrointestinal side effects (nausea and vomiting).

11. Subject Safety and Data Monitoring

Monitoring of the patients will abide by the standards set forth by the American Society of Anesthesiology. Additionally, the standard surgical procedures will be applied in this study.

Any adverse event will be reported immediately to the IRB and FDA if it was drug related. Given that the medications used in this study are used routinely by anesthesiologists, the reported adverse event will unlikely be related to the study itself.

12. Procedures to Maintain Confidentiality

As a patient enters the study, the investigator will assign that patient to the next sequential study code number available. All data and subject information will be stored in the investigator's laboratory in locked file cabinets or on a secure computer. Access to the data will be restricted to the investigators, nurses, and technicians involved in this project.

13. Potential Benefits

The main benefit is that if there is a difference between the groups then they will have less blood loss. The choice of medication for blood pressure control intraoperatively will likely be implemented should the results demonstrate any difference between the groups. In the event that there was no difference between the groups, then the medications can continue to be used without the concern of impaired visibility to the endoscopic surgeon.

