Statistical Analysis Plan: Title Page

**Blood Loss and Visibility with Esmolol vs. Labetalol in Endoscopic Sinus Surgery: A
Randomized Trial**

Date: 09/04/2018

Study Summary and Aims

The purpose of this study is to compare esmolol and labetalol bleeding and visibility outcomes in FESS surgery. It is a double-blinded two-armed trial with no placebo control, conducted at a tertiary center. Participants include adults with history of CRS with or without nasal polyps, undergoing FESS for CRS. 38 patients were enrolled, with 32 receiving study drug (17 esmolol, 15 labetalol). Total study duration, including recruitment and analysis, was 1 year with no follow-up. Treatments involve giving intraoperative 20mg of Labetol (max dose = 300 mg for total operation) or infusing 0.1mg/kg/min esmolol (max dose after 30 minutes = 0.3mg/kg/min) when MAP rises above 80 mmHg. The primary aim is to evaluate the relative efficacy of these drugs in FESS surgery, specifically controlling bleeding and improving visibility.

Study Endpoints

March 2017 – March 2018 enrollment, drug administration only during surgery.

Sample Size Considerations

Futility analysis based on estimated blood loss data to see how many patients would be required to show significant differences in blood loss, and therefore mucosal visibility, between drug groups. Given the small differences in blood loss per minute during surgery between treatment groups (0.63 compared to 0.67), and given the relatively large standard deviations obtained (0.33 and 0.37), 1,245 patients would be required in each drug group (total N = 2,490), using a non-paired (two-sided) *t-test* for the comparison, to show a statistically significant difference between the 2 treatments with a power of 0.8 and type I error of 0.05.

These sample size calculations are based on the primary aims of determining a significant difference in FESS visibility between the two drugs.

The null hypothesis is that there will be no statistical difference between esmolol and labetalol in FESS visibility and bleeding parameters. The alternative hypothesis is that there will be a significant difference, in either drug, for improved FESS visibility and bleeding parameters.

The minimum difference that we judge to be statistically significant is a 1-point change on the visibility scores (Boezaart 5-point, Wormald 10-point).

Analysis Sets

N/A

Statistical Analysis and Description of Main Tables

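### The anesthesiologist's exclusion rule is not confined to the time before assignment, and the SAP defines no analysis set to keep excluded patients in their arm

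*Protocol*

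**What the plan says.** The protocol gives the anesthesiologist's power to exclude in two forms.

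- Section 3: "Subjects may be excluded from the study if the anesthesiologist deemed it necessary that the protocol drug can not be used on the patient", with the sentence going on to accept any reason. Section 7 repeats this for cases where the "anesthesiologist deemed it necessary that the protocol drug cannot be used on the patient for any reason".
- Section 4, at the end of its list of exclusion criteria: "any patient that the anesthesiologist deems unfit for randomization will also be excluded".

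On blinding, Section 4 says "study drug will be blinded for surgeon". It also describes the rhinologist as blinded and the videos as de-identified. For the drug itself it says "If randomized, the anesthesiology investigator will obtain 3 bottles of labetalol (100 mg in 10 mL", with a parallel instruction for esmolol. The SAP, under Study Summary and Aims, says "It is a double-blinded two-armed trial with no placebo control" and does not name the blinded parties.

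On numbers, Section 4 says "We will randomize the patients in blocks of 4", with 20 planned per arm. The SAP reports "38 patients were enrolled, with 32 receiving study drug (17 esmolol, 15 labetalol". Its Analysis Sets entry is N/A, and both table shells are headed 13 and 15 patients.

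**The concern.** Fitness for randomization can only be judged before assignment. Whether the protocol drug, in the singular, can be used may be judged at any time, including once it is known which drug that is. Esmolol and labetalol differ in receptor profile and in how they are given, so patients judged unsuitable for one need not resemble those judged unsuitable for the other. If such patients leave the study after assignment, the arms are no longer protected by randomization for either blood loss or visibility. An analysis of all randomized patients as assigned would limit the damage, but the SAP specifies none.

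**Working it through.** The plan states no figure on this point, so there is nothing to reproduce. The check sets the texts side by side, counts patients and illustrates the size.

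**1. Timing.** Section 4 fixes the judgement before randomization. Sections 3 and 7 set no time limit. Nothing says whether these are one rule or two, or which governs.

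**2. Knowledge of the arm.** The blinding stated in the protocol covers the surgeon, the rhinologist and the video review. The anesthesiology investigator obtains the named drug. Labetalol is given as slow intravenous aliquots plus infusion, esmolol as a diluted infusion, and no dummy is described. That the anesthesiologist can know the arm is an inference from this, and the SAP's double-blind label conflicts with it.

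**3. Counts (SAP).**
- Without study drug: 38 − 32 = 6, and 6/38 = 15.8%.
- Treated: 17 + 15 = 32. Table shells: 13 + 15 = 28. Treated but outside the shells: 4, and 4/32 = 12.5%.
- The groups are not identified. If Group A is esmolol, the four are 4/17 against 0/15 labetalol. If Group A is labetalol, they are 2/15 labetalol and 2/17 esmolol.

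**4. Illustration for the six without drug.** Assumptions: all 38 were randomized, in one sequence of blocks of 4; patients left out bled D more on average than those kept, with the same D in both arms; D = 1 SD, with the protocol's 150 and 200 mL (Section 14) taken in turn as the SD.

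Nine full blocks give 18 and 18. The two remaining patients make the arms 18/20, 19/19 or 20/18 (esmolol/labetalol).

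If a fraction f of an arm is left out, the full-arm mean is (1 − f)K + f(K + D) = K + fD, where K is the mean of those kept. Leaving them out therefore lowers the arm mean by fD, and the between-arm difference shifts by (f for labetalol − f for esmolol) × D.

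| Arms E/L | Left out E | Left out L | Net shift | mL at SD 150 to 200 | Share of 110 mL |
|---|---|---|---|---|---|
| 18/20 | 1/18 = 0.056 | 5/20 = 0.250 | 0.194 SD | 29.2 to 38.9 | 27% to 35% |
| 19/19 | 2/19 = 0.105 | 4/19 = 0.211 | 0.105 SD | 15.8 to 21.1 | 14% to 19% |
| 20/18 | 3/20 = 0.150 | 3/18 = 0.167 | 0.017 SD | 2.5 to 3.3 | 2% to 3% |

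Under this assumption the shift disfavours esmolol in every row. It reverses if those left out bled less, and at D = 0 it is zero.

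**The case against.** The strongest reply is that there is only one rule. Section 7 places the sentence among the exclusion criteria, beside pregnancy, asthma and BMI. Section 4 puts its version at the end of the same list. The protocol drug may be meant generically. No passage gives a reason for exclusion that applies to one drug only, and the listed cardiac and pulmonary exclusions apply to both arms. This reading is available and stands as a reason for moderation. It does not remove the point, because the wording of Sections 3 and 7 also permits the later reading and nothing excludes it.

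The unblinding is also inferred. The exclusion rule names the anesthesiologist, while the drug is obtained by the anesthesiology investigator, and the documents do not say whether these are the same person. That stands too, and it is why the SAP's label has to be reconciled with the protocol.

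A reader might infer that the six patients without drug were removed under this rule. The documents do not support that. Under Section 4 the drug is given only when sevoflurane is at its maximum and the pressure target is still missed, so some or all of the six may simply never have needed it. The trial profile, where reasons might appear, is not in the available text.

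A reader might also shift only the arm that lost more: 4/19 × 1 SD = 0.21 SD, or 32 to 42 mL, which is 29% to 38% of 110 mL. This ignores the two left out of the other arm. Counting both halves the figure.

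**Conclusion.** The concern holds as a timing ambiguity with no analysis set behind it. Sections 3 and 7 as worded allow a randomized patient to be dropped from the study, probably by someone able to know the arm, and the SAP has no rule that would keep that patient in the comparison. The documents do not establish that this happened, that reasons differed by arm, or that the anesthesiologist was in fact unblinded.

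The illustrated shift in mean blood loss is 0.02 to 0.19 SD, about 3 to 39 mL against the planned 110 mL. It rests on all 38 having been randomized in one blocked sequence and on an assumed 1 SD gap in both arms. It is zero without an association between leaving out and bleeding. The four treated patients outside the table shells are a further unexplained gap and are not attributed to this rule. It should be fixed, with medium confidence.

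**What to change.** **Protocol Sections 3, 4 and 7.** Replace the two forms with one rule: before the assignment is opened, the anesthesiologist confirms that the patient may receive either study drug, and exclusion from the study is possible only at that point. Later clinical care, including withholding the assigned drug, stays at the anesthesiologist's discretion and does not end participation.

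**SAP, Analysis Sets.** Replace N/A with a primary set of all randomized patients, analysed in the assigned arm. Include those whose drug was withheld and those who never met the pressure trigger. Score visibility and blood loss for all of them, and report reasons for receiving no drug by arm. An analysis of treated patients may be kept as supportive. Account for the difference between 32 treated and 28 in the table shells.

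**Blinding.** State in both documents who is blinded, so that the SAP's label agrees with the protocol.

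**Cost.** Some wording, one line on the eligibility form, and outcome collection on a few patients who are having the surgery anyway. Patients without drug will slightly dilute the contrast. The SAP is dated after its stated enrolment period (March 2017 to March 2018), so for patients already enrolled only the analysis set and the reporting can still change. Where outcomes were not collected, that should be reported by arm.
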